### **3.3.3 Exclusion criteria**

Subjects will not be allowed to participate if any of the following general criteria apply:

1. Any finding in the medical examination (including BP, PR or ECG) is deviating from normal and judged as clinically relevant by the investigator
2. Repeated measurement of systolic blood pressure outside the range of 90 to 140 mmHg, diastolic blood pressure outside the range of 50 to 90 mmHg, or pulse rate outside the range of 50 to 90 bpm
3. Any laboratory value outside the reference range that the investigator considers to be of clinical relevance
4. Any evidence of a concomitant disease judged as clinically relevant by the investigator
5. Gastrointestinal, hepatic, renal, respiratory, cardiovascular, metabolic, immunological or hormonal disorders
6. Cholecystectomy and/or surgery of the gastrointestinal tract that could interfere with the pharmacokinetics of the trial medication (except appendectomy and simple hernia repair)
7. Diseases of the central nervous system (including but not limited to any kind of seizures or stroke), and other relevant neurological or psychiatric disorders
8. History of relevant orthostatic hypotension, fainting spells, or blackouts
9. Chronic or relevant acute infections
10. History of relevant allergy or hypersensitivity (including allergy to the trial medication or its excipients)
11. Intake of drugs with a long half-life (more than 24 h) within 30 days or less than 10 half-lives of the respective drug prior to administration of trial medication
12. Within 10 days prior to administration of trial medication, use of drugs that might reasonably influence the results of the trial or that might prolong the QT/QTc interval
13. Participation in another trial where an investigational drug has been administered within 60 days prior to planned administration of trial medication
14. Used nicotine-containing products (e.g., cigarettes, cigars, chewing tobacco, snuff) within 6 weeks before screening and unable to abstain from using these products until study completion
15. Alcohol abuse (consumption of more than 20 g per day for females and 30 g per day for males)
16. Drug abuse or positive drug screening
17. Blood donation of more than 100 mL within 30 days prior to administration of trial medication or intended donation during the trial
18. Intention to perform excessive physical activities within one week prior to administration of trial medication or during the trial
19. Inability to comply with dietary regimen of trial site
20. A marked baseline prolongation of QT/QTcB interval (such as QTc intervals that are repeatedly greater than 450 ms in males or repeatedly greater than 470 ms in females) or any other relevant ECG finding at screening

21. A history of additional risk factors for Torsades de Pointes (such as heart failure, hypokalemia, or family history of Long QT Syndrome)
22. Subject is assessed as unsuitable for inclusion by the investigator, for instance, because considered not able to understand and comply with study requirements, or has a condition that would not allow safe participation in the study
23. Detection of cataract in slit lamp examination
24. GFR according to CKD-EPI-Formula  $< 90$  mL/min at screening [[R12-1392](#)]

**Female subjects will not be allowed to participate if any of the following applies:**

25. Females who are not surgically sterilised or who are not postmenopausal, defined as at least 1 year of spontaneous amenorrhea (in questionable cases a blood sample with simultaneous levels of FSH above 40 U/L and estradiol below 30 ng/L is confirmatory)
26. Positive pregnancy test
27. Lactation period

For study restrictions, refer to [Section 4.2.2](#).

### **3.3.4 Removal of subjects from therapy or assessments**

#### **3.3.4.1 Removal of individual subjects**

An individual subject is to be removed from the trial if:

1. The subject withdraws consent for trial treatment or trial participation, without the need to justify the decision
2. The subject needs to take concomitant drugs that interfere with the investigational product or other trial medication
3. The subject is no longer able to participate for other medical reasons (such as pregnancy, surgery, adverse events, or diseases)
4. An AE or clinically significant laboratory change or abnormality occurred that the investigator judges to warrant discontinuation of treatment. This may include cases of sustained symptomatic hypotension (BP  $< 90/50$  mmHg) or hypertension (BP  $> 180/100$  mmHg) or of clinically relevant changes in ECG requiring intervention as well as unexplained liver enzyme elevations at any time during the trial.
5. The subject shows an elevation of AST and/or ALT  $\geq 3$ -fold ULN combined with an elevation of total bilirubin  $\geq 2$ -fold ULN (measured in the same blood sample) and/or needs to be followed up according to the 'DILI checklist' provided in the ISF.
6. Relevant individual QT prolongation, i.e. a QTcB increase of greater 60 ms from baseline in connection with absolute QT or QTc greater than 500 ms, which has been confirmed by a repeat ECG recording.
7. eGFR calculated with the CKD-EPI formula is determined to be below 80 ml/min on 2 consecutive assessments 24 h apart
8. If a patient develops symptoms of muscle or tissue injury (e.g., muscle aches, dark urine or other signs of rhabdomyolysis), in line with clinically significant increased CK levels.

9. Neutropenia will lead to individual discontinuation from trial medication if any of the following applies:
  - Febrile Neutropenia at any time, i.e. absolute neutrophil count (ANC) below lower limit of normal with concomitant body temperature greater or equal 38 degrees C
  - ANC below 1000/microliter at any time
  - ANC below 1500/microliter (but greater 1000/microliter) if still present after 1 week
10. Leukopenia will lead to individual discontinuation from trial medication if any of the following applies:
  - Febrile leukopenia at any time, i.e. absolute lymphocyte count (ALC) below lower limit of normal with concomitant body temperature greater or equal 38 degrees C
  - ALC below 2500/microliter at any time
  - ALC below 3000/microliter (but greater 2500/microliter) if still present after 1 week
11. Thrombocytopenia will lead to individual discontinuation from trial medication if any of the following applies:
  - Thrombocytopenia, i.e. absolute platelet count (APC) below lower limit of normal at any time if associated with clinical signs or symptoms of bleeding
  - APC below 80,000/microliter at any time
  - APC below 100,000/microliter (but greater 80,000/microliter) if still present after 1 week

In addition to these criteria, the physician may discontinue subjects at any time based on his or her clinical judgment.

A subject can also be removed from the trial if eligibility criteria are being violated or if the subject fails to comply with the protocol (for instance, by non-adherence to dietary rules, or non-attendance at study assessments).

If a subject is removed from or withdraws from the trial prior to first administration of trial medication, the data of this subject will not be entered in the case report form (CRF) or trial database and will not be reported in the clinical trial report (CTR). If a subject is removed from or withdraws from the trial after first administration of trial medication, this will be documented and the reason for discontinuation must be recorded in the CRF. In this case, the data will be included in the CRF/trial database and will be reported in the CTR. At the time of discontinuation a complete end of trial examination will be performed if possible and the information will be recorded in the CRFs. If the discontinuation occurs before the end of the REP (see [Section 5.2.2.2](#)), the discontinued subject should if possible be questioned for AEs and concomitant therapies at or after the end of the REP in order to ascertain collection of AEs and concomitant therapies throughout the REP, if not contrary to any consent withdrawal of the subject. These discontinuations will be discussed in the CTR.

If it is known that a subject becomes pregnant during the trial, administration of the trial medication has to be stopped immediately, and the subject has to be removed from the trial. The subject is to be followed until she has given birth or until the end of pregnancy. The subject's data are to be collected until the end of the trial (last visit of last subject) and reported in the clinical trial report. For reporting of pregnancy and all related events refer to [Section 5.2.2.2](#).

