The minimum data set for review consists of the following data:

- AEs in the current and, if applicable, preceding dose groups (including clinically relevant findings from ancillary safety testing listed below) (Note: AEs may be ongoing at the time of Safety Reviews and AE information may be subject to change prior to Database Lock)
- Results from 12-lead EGG in the current and preceding dose groups.
- Vital signs in the current and preceding dose groups
- Clinical laboratory tests in the current and preceding dose groups
- Check of criteria for stopping subject treatment as per [Section 3.3.4.1](#)
- PK data including extrapolation to support conclusions about safety margins (not required for inclusion of second cohort of the 10 mg dose group since based on the results from the previous SRD/MRD study (see [Section 1.2.5](#)) exposure is not expected to exceed  $C_{max}$  and 1/2 of the AUC of the 4-week rat toxicology study at NOAEL.

The decision to continue with the next cohort at the same dose level or the next higher dose level will be made jointly by the Principal Investigator (or an authorised deputy) and the trial clinical monitor (or an authorised deputy) based on the criteria described in [Section 2.3](#). In-depth analysis includes preliminary PK data, if possible extrapolations of exposure for the current and any new cohorts, all available safety data, especially SAEs (if occurred), AEs fulfilling stopping criteria, other AEs and out-of-range laboratory results (if considered clinically significant) and ECG results. Safety Reviews can be conducted face-to-face or by video/telephone conference. The trial clinical monitor is responsible for organizing and minuting the reviews. Minutes will be signed off by the Principal Investigator (or an authorised deputy) and filed in the ISF and TMF.

To proceed to the next higher dose level at least data up to Day 28 from 10 evaluable subjects of the preceding dose level (with at least 7 subjects on active treatment) are required.

The investigator (after consultation with the sponsor) is allowed to alter the scheduled dose levels within the planned dose range on the basis of experience gained during the study.

An overview of all relevant trial activities is provided in the [Flow Chart](#). For visit schedules and details of trial procedures at selected visits, refer to [Sections 6.1](#) and [6.2](#), respectively.

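### Section 3.3.4.1 makes every stopping criterion a removal from the trial, so a still-consenting subject who stops dosing early has no stated path onto the post-last-dose visits

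*Protocol*

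**What the plan says.** Section 3.3.4.1 opens with "An individual subject is to be removed from the trial if" and lists 11 items under it.

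- Item 1 names two kinds of consent and gives both the same consequence: "The subject withdraws consent for trial treatment or trial participation, without the need to justify the decision".
- Item 4 concerns an event that "the investigator judges to warrant discontinuation of treatment".
- Items 9-11 (neutropenia, leukopenia, thrombocytopenia) are worded as medication stops. Item 9 reads "Neutropenia will lead to individual discontinuation from trial medication if any of the following applies".
- Section 3.1, in the minimum data set for safety reviews, describes the same list as stopping rules for treatment: "Check of criteria for stopping subject treatment as per".
- The pregnancy rule in Section 3.3.4.1 names two separate steps: "administration of the trial medication has to be stopped immediately, and the subject has to be removed from the trial".

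For a subject who leaves after the first dose, Section 3.3.4.1 states: "At the time of discontinuation a complete end of trial examination will be performed if possible and the information will be recorded in the CRFs". When this happens before the residual effect period (REP) is over, "the discontinued subject should if possible be questioned for AEs and concomitant therapies at or after the end of the REP". Section 6.2.3 likewise directs subjects who stop treatment early to the EOT visit. Section 5.2.2.2 says that the length of the REP is unknown, and that active AE monitoring is not required after a subject's own end of trial.

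**The concern.** Stopping the drug and leaving the trial are different events, and the protocol's wording shows that its authors knew this. Even so, the operative sentence gives both the same result. A volunteer whose neutrophil count meets item 9 but who is willing to keep attending is, on the text, removed from the trial and given the EOT examination on leaving.

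These subjects are few, but their time course after the last dose is of particular interest. The duration of drug levels and PD effects after dosing is stated to be unknown. The rationale for Amendment 3 adds that steady state had not been reached after 4 weeks at 10 mg. The causality guidance in Section 5.2.2.1 also relies on what happens after the drug is withdrawn. An EOT examination at discontinuation may fall while drug or effect is still present, with no scheduled PK sample to show it.

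**Working it through.** No sample-size or power formula applies. The check is a count of Flow Chart rows set beside the removal rules.

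**Inputs (Flow Chart).** The last dose is on Day 28 at 648 h. Ambulatory visits after the Day 29 discharge are on Days 30, 31, 32, 34, 36, 38 and 40. EOT is on Days 42-48.

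**Times.** Planned hour = 24 × (day − 1), which reproduces the Flow Chart's own hours: 696, 720, 744, 792, 840, 888 and 936. Subtracting 648 gives 48, 72, 96, 144, 192, 240 and 288 h after the last dose. EOT falls 42 − 28 = 14 to 48 − 28 = 20 days after the last dose.

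**Assessments on the 7 visits.**
- PK blood: all 7 days.
- PD blood: Days 30, 32, 34, 36, 38 and 40 = 6.
- AE questioning: Days 30, 31, 32 and 34 = 4.
- Laboratory, ECG and vital signs together: Day 30 only = 1.

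**EOT row and footnote 4.** Laboratory, PD, ECG, vital signs and AE questioning are present. PK is not. No visit is planned after EOT.

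**Comparison from Day 30 (or its equivalent) onward, with the stopping rule taken literally:**

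| Scheduled item | Completer | Stopped during dosing |
|---|---|---|
| PK samples | 7 | 0 |
| PD samples (visits + EOT) | 6 + 1 = 7 | 0 + 1 = 1 |
| AE questioning on washout visits | 4 | 0 |
| Laboratory/ECG/vital-sign sets (visits + EOT) | 1 + 1 = 2 | 0 + 1 = 1 |
| Last slit-lamp examination (Section 5.2.5.3) | 14-20 days after last dose | at discontinuation |

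The stopped subject also has the later AE and concomitant-therapy questioning, to be done where possible. It has no fixed date because the REP has no stated length.

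**Frequency.** The protocol gives no event rate. The Amendment 3 rationale reports that all subjects in the 10 mg group completed treatment. One stopped active subject would be 1 of 9 at that dose (1/9 = 11%).

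**Blood volume.** 7 × 2.7 mL = 18.9 mL, against the limit of 510 mL per subject. These samples are already scheduled for every subject.

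**The case against.** The strongest reply is that the text gives one workable rule. All items share one consequence. The phrase in item 4 can be read as the trigger, not as a competing consequence, and stopping medication under items 9-11 is compatible with removal. Sections 3.3.4.1 and 6.2.3 agree on the EOT examination. This stands to the extent that no two sentences demand opposite actions. The fault is a consequence set too broadly.

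It can also be said that the loss is inferred. No sentence says that sampling stops, and Section 6.2.3 does not limit the subject to the EOT visit. Flow Chart footnote 9 and Section 5.5 allow added PK samples and visits within 510 mL. This also stands, and it limits the size of the point. That allowance, however, is a general power to adapt sampling during the trial, which Section 5.5 says is exercised through a protocol amendment. It is not a standing instruction for a stopped subject.

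Safety follow-up is largely covered. Section 5.2.2.2 has AEs collected through the REP until the individual end of trial and requires persisting AEs to be followed. Section 6.2.3 has clinically relevant abnormal values monitored until acceptable. All of this stands.

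A reader might infer more than the documents support:
- **Different handling between sites.** The Synopsis names one trial site and one principal investigator.
- **A criterion first met at the Day 30 laboratory would end the remaining visits.** The EOT rule in Section 6.2.3 covers only subjects who stop before the planned treatment period ends, so it does not reach this case.
- **Bias in the main endpoints.** The primary endpoint counts subjects, and one stopped for a drug-related AE is already counted. The Day 28 PK endpoints are complete by 672 h, or cannot exist once dosing has stopped.

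**Conclusion.** The point holds as a minor one. The protocol applies removal from the trial to criteria that it words as stopping treatment or medication, and to withdrawal of consent for treatment only. In the text shown, nothing keeps a consenting subject who stops early on the post-last-dose schedule. For each such subject, up to 7 PK samples, 6 PD samples, 4 AE questionings and 1 laboratory/ECG/vital-sign set are left without a stated basis. The EOT examination moves from 14-20 days after the last dose to the time of discontinuation. The loss is mainly washout PK/PD and scheduled late safety checks in a few subjects. It is not a loss of all follow-up.

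This rests on two assumptions. The first is that investigators follow the lead sentence of Section 3.3.4.1 literally. The second is that parts not available here (Sections 2.3, 3.3.5 and 5.6, and the liver-injury checklist cited in item 5) do not already keep such subjects on follow-up.

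**What to change.** State in Sections 3.3.4.1 and 6.2.3 that:

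- items 4-11, and withdrawal of consent for treatment only, stop trial medication;
- of the two kinds of consent withdrawal in item 1, only withdrawal from participation ends participation;
- subjects who still consent keep the existing post-last-dose safety, PK and PD visits, timed from their own last dose (48 to 288 h), with EOT 14-20 days after that dose, unless the investigator judges this medically inappropriate.

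Items 2 and 3 and the pregnancy rule can stay as they are.

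The cost is a wording change. It adds no new type of visit and no blood beyond what is already planned for each subject. The downside is up to 7 short visits and a later EOT for a healthy volunteer who has stopped the drug, and some may decline.

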### **5.2.3 Assessment of safety laboratory parameters**

For the assessment of laboratory parameters, blood and urine samples will be collected by the trial site at the time points indicated in the [Flow Chart](#) after the subjects have fasted for at least 10 h. Overnight fasting is not required at the discretion of the investigator or designee for retests.

The parameters that will be determined are listed in [Tables 5.2.3: 1](#) and [5.2.3: 2](#). Reference ranges will be provided in the ISF, Section 10.

Manual differential white blood cell count or urine sediment examinations will only be performed if there is a clinically relevant abnormality in the automatic blood cell count or in the urinalysis, respectively.

Table 5.2.3: 1 Routine laboratory tests

Functional lab group	Test name
Haematology	Haematocrit
	Haemoglobin
	Red blood cell count (RBC)
	White blood cell count (WBC)
	Platelet count
Automatic WBC differential (relative and absolute)	Neutrophils, eosinophils, basophils, monocytes, lymphocytes
Manual differential WBC (if automatic differential WBC is clinically relevant abnormal)	Polymorphnuclear neutrophils (segs), band neutrophils (stabs), eosinophils, basophils, monocytes, lymphocytes
Coagulation	Activated partial thromboplastin time (aPTT)
	Prothrombin time (Quick's test and INR)
	Fibrinogen
Enzymes	Aspartate transaminase (AST/GOT)
	Alanine transaminase (ALT/GPT)
	Alkaline phosphatase (AP)
	Gamma-glutamyl transferase (GGT)
	Glutamate dehydrogenase (GLDH)
	Creatine kinase (CK)
	CK-MB, only if CK is elevated
	Lactate dehydrogenase (LDH)
	Lipase
	Amylase
Hormones 	Thyroid stimulating hormone (TSH)
	fT3, fT4
	FSH 
Substrates 	Plasma glucose
	Creatinine
	eGFR (derived from creatinine using CKD-EPI formula)
	Cystatine
	Total bilirubin
	Direct bilirubin
	Total protein
	Protein electrophoresis (only at screening examination)
	Albumin
	Alpha-1-Globulin
	Alpha-2-Globulin
	Beta-Globulin
	Gamma-Globulin
	C-Reactive Protein (CRP)
	Uric acid
	Total cholesterol
Triglycerides	
Electrolytes	Sodium
	Potassium
	Chloride
	Calcium
	Inorganic phosphate

Table 5.2.3: 1 Routine laboratory tests (cont).

Functional lab group	Test name
Urinalysis (Stix)	Urine nitrite Urine protein Urine glucose Urine ketone Urobilinogen Urine bilirubin Urine erythrocytes Urine leukocytes Urine pH

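### The leukopenia removal rule (Protocol 3.3.4.1, item 10) is set on the lymphocyte count, so its numeric triggers remove subjects whose white cell count is above both cut-offs

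*Protocol*

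**What the plan says.** Section 3.3.4.1 lists the conditions under which an individual subject has to be removed. Item 10 names leukopenia and makes discontinuation of trial medication mandatory when any one of three bullets is met:

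- "Febrile leukopenia at any time, i.e. absolute lymphocyte count (ALC) below lower limit of normal", combined with a body temperature of 38 degrees C or more
- "ALC below 2500/microliter at any time"
- "ALC below 3000/microliter (but greater 2500/microliter) if still present after 1 week"

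Items 9 and 11 follow the same template. Item 9 (neutropenia) is judged on "absolute neutrophil count (ANC) below lower limit of normal" and on numeric neutrophil limits. Item 11 (thrombocytopenia) is judged on "absolute platelet count (APC) below lower limit of normal at any time" with bleeding, and on numeric platelet limits.

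Table 5.2.3: 1 lists WBC as a haematology test in its own right. The automatic differential, given in relative and absolute terms, consists of "Neutrophils, eosinophils, basophils, monocytes, lymphocytes". The protocol nowhere redefines ALC and gives no WBC threshold for leukopenia. Reference ranges are left to the investigator site file.

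**The concern.** Leukopenia is a low total white cell count. A low lymphocyte count is a different condition. Item 10 names the first and measures the second, and it is the only one of the three haematology rules in which heading and variable disagree.

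The site is left with two readings of a mandatory safety rule. Taken literally, a subject must stop treatment on a lymphocyte value that says little about total WBC, and the withdrawal is then attributed to leukopenia. If the site reads the item as leukocytes, it departs from the written text. Checking the stopping criteria is part of the minimum data set for every Safety Review (Section 3.1), so the choice of reading recurs at each review. The Amendment 3 rationale in Section 11 leaves the individual discontinuation criteria unchanged, so the wording also governs the 15 mg and 20 mg groups.

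**Working it through.** The plan gives no figure to reproduce here. The check compares what the rule catches as written with what it would catch on WBC at the same cut-offs.

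**Inputs.** Cut-offs of 2500 and 3000/microliter (item 10). A neutrophil count (ANC) of 1500 meets no numeric trigger in item 9, because the higher limit there is "ANC below 1500/microliter (but greater 1000/microliter) if still present after 1 week". Lymphocytes and neutrophils are two of the five parts of WBC (Table 5.2.3: 1).

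**Relations.** WBC ≥ ALC + ANC, and ALC ≤ WBC.

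**Step 1: does the literal rule catch subjects above the cut-offs on WBC?** Take ALC 2499 and ANC 1500.

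- WBC ≥ 2499 + 1500 = 3999
- 3999 − 2500 = 1499 above the lower cut-off
- 3999 − 3000 = 999 above the upper cut-off

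The ALC trigger fires, while neither numeric trigger would fire on WBC. More generally, with ANC of at least 1500, any ALC from 3000 − 1500 = 1500 up to 2499 gives WBC of at least 3000 and still requires discontinuation.

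**Step 2: the same point as a share of WBC.** The trigger fires when lymphocytes fall below cut-off ÷ WBC.

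| WBC (/microliter) | Share below which ALC < 2500 | Share below which ALC < 3000 |
|---|---|---|
| 5000 | 50.0% | 60.0% |
| 6000 | 41.7% | 50.0% |
| 7000 | 35.7% | 42.9% |
| 8000 | 31.2% | 37.5% |
| 10000 | 25.0% | 30.0% |

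The protocol gives no lymphocyte share. If it is assumed to lie between 20% and 40%, ALC at WBC 6000 is 1200 to 2400, and the 2500 trigger fires across that whole range. The entry criteria set no numeric minimum for ALC. Exclusion criterion 3 applies only to out-of-range values that the investigator considers clinically relevant.

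**Step 3: does the literal rule miss anyone on the numeric triggers?** Since ALC ≤ WBC, WBC below 2500 implies ALC below 2500, and WBC below 3000 implies ALC below 3000. A WBC that stays below 3000 for a week is therefore caught at once if ALC is below 2500, and otherwise after the week. (An ALC of exactly 2500 falls between the two bullets, but that comes from the template, not from the choice of variable.) The numeric error runs in one direction, towards extra withdrawals.

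**Step 4: effect on escalation.** A dose group has 12 subjects, 9 on active drug. Section 3.1 requires 10 evaluable subjects with at least 7 on active drug. One removal leaves 12 − 1 = 11, with at least 9 − 1 = 8 active. Two leave 10, with at least 7 active. The requirement still holds in both cases, before the replacement blocks in Section 7.5 are used.

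**The case against.** The strongest defence is that the heading makes leukopenia a precondition and the bullets only refine it. This fails on the text. The first bullet defines febrile leukopenia through the lymphocyte count, items 9 and 11 also use their bullets as the definition, and a precondition would need a WBC threshold that the protocol does not supply.

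A second defence is that the rule errs on the side of caution. For the two numeric triggers that is correct and limits the seriousness of the point. It does not justify mandatory removal of subjects who lack the named condition.

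Several stronger readings are tempting, and the documents do not support them:

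- *The subject in Step 1 has a normal white count.* A WBC of 3999 is shown only to exceed the 2500 and 3000 cut-offs. Whether it is normal depends on the laboratory's lower limit, which is not in the protocol.
- *A febrile subject with low WBC and normal lymphocytes goes unprotected.* To escape both the 2500 trigger and item 9's febrile trigger, the subject needs ALC of at least 2500 and ANC at or above its lower limit. If that limit is assumed to be 1500 to 2000, WBC is at least 4000 to 4500, so the gap exists only if the laboratory's WBC limit is higher still. Items 3 and 4, and the physician's general discretion in the same section, also allow removal.
- *Cohorts would be halted.* Section 3.3.4.2 item 6 counts adverse events that meet stopping criteria in at least two subjects on active drug at one dose level. Under Section 5.2.2.2 a laboratory change is recorded as an adverse event only if judged clinically relevant. No halt probability follows from the protocol.
- *The completed 10 mg group settles the matter.* Section 11 reports that all its subjects completed treatment per protocol. Either none met the literal triggers during treatment or another reading was used; the text does not say which.

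**Conclusion.** The point holds: item 10 names leukopenia and measures lymphocytes. That conclusion rests on the protocol's own wording and on lymphocytes being a component of WBC. The Step 1 arithmetic needs no outside figure; only the 20% to 40% illustration in Step 2 is assumed.

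The size is limited. The numeric triggers can only add withdrawals. How many they add depends on the subjects' lymphocyte counts, which the protocol does not give. A reader might infer that dose escalation is put at risk, but Step 4 shows that one or even two removals in a group of 12 leave the escalation condition satisfiable.

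The protocol does not state outright which word is the slip. The heading, and the description of the added rule as a leukopenia threshold in the Amendment 1 log, make the variable the likelier one. This should be fixed because it is a mandatory safety rule that cannot be applied as both its heading and its bullets say.

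**What to change.** The sponsor should first confirm that leukopenia is the intended condition. If so, replace the absolute lymphocyte count and its abbreviation with total white blood cell count (WBC) in all three bullets of item 10, and keep the cut-offs of 2500 and 3000/microliter. Only if lymphopenia was intended should the item instead be retitled, with lymphocyte-specific cut-offs set below the laboratory's lower limit of normal for lymphocytes.

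No new test is needed, because WBC and the differential are already measured. The cost is a protocol amendment, with the approval that a change to a safety rule requires. Moving to WBC makes the numeric rule looser than its current literal wording, and the amendment should say so openly.
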